6.1.1 Treatment Schedule

If chemotherapy is going to be used, the preferred sequence is vaginal cuff brachytherapy first; however, treatment sequence may be determined at the investigator's discretion.

It is recommended that patients begin cuff brachytherapy within 16 weeks of hysterectomy. In the event chemotherapy precedes brachytherapy, it is recommended that brachytherapy begins 2-6 weeks after completion of chemotherapy.

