APPENDIX I. Health Care Expense Survey

Health Care Expense Survey

Patient Study ID: _____

Patient Initials: _____

Date of Completion: _____ / _____ / _____

Health Care Expense Survey

Before you were diagnosed with endometrial cancer, did you do paid or unpaid work outside the home?

Yes No

If you worked outside the home, which of the following best applies to you?

Paid work outside the home Yes No

Unpaid work outside the home Yes No (including work in a family farm or business).

Self-employed / business owner Yes No

If you worked outside the home:

How many days per week did you work? ____ (days)

How many hours per day did you work? ____ (hours)

What is your profession?

In what industry do you work?

What is / was your job title?

NOTE: This section is designed to capture the out of pocket expenses associated with radiation therapy.

How many hours were spent in total for each radiation treatment (time from leaving home/other accommodation or work to return to home/other accommodation or work)?

____ (hours)

What is the distance from the radiation treatment facility from home/other accommodation or work? ____ (miles)

Did you commute daily to radiation treatment from your home? Yes No

(If yes), method of transport used to get to the radiation therapy facility (Check all that apply)

Car Yes No

(If yes) approximate cost for parking per visit \$_____.____

Did you drive yourself? Yes No

Were you driven? Yes No

Was it a combination of driving yourself or being driven Yes No

Shuttle Yes No

(If yes) Approximate cost per visit \$_____.____

Public transport Yes No

(If yes) Approximate cost per visit \$_____.____

On foot Yes No

Taxi/car service Yes No

(If yes) Approximate cost per visit (both ways) \$_____.____

(If no), which of the follow apply (check one):

I was in a health care facility during radiation

I was living with a friend/family member during radiation (answer the commuting questions above)

I stayed hotel, apartment, or similar facility during radiation (answer the commuting questions above)

If hotel, apartment or similar facility, estimated cost of lodging during your radiation treatment \$_____.____

Number of radiation treatments during which at least one other person accompanied patient ____

Number of visits to radiation treatment facility since completing radiation therapy (follow up visits) ____

From the 1st day of starting radiation, until 40 days after the completion of radiation:

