Number of days the patient was unable to go to work at all ____

Number of days the patient went to work part-time ____

If part time, number of hours reduced from typical work day ____

Estimate child care costs due to radiation therapy \$____, ____

Estimate wages lost due to radiation therapy \$____, ____

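### Appendix I counts days off work after radiation starts without asking the cause, or whether the woman was at work when radiation began

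*Combined protocol and SAP*

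**What the plan says.** Appendix I opens its work questions with "Before you were diagnosed with endometrial cancer, did you do paid or unpaid work outside the home". Usual days and hours, profession, industry and job title follow. No item asks whether the woman was working, or on leave, when radiation began.

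After the transport and lodging items, the form sets a window: "From the 1st day of starting radiation, until 40 days after the completion of radiation". Four kinds of loss are asked for in that block:

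- "Number of days the patient was unable to go to work at all": no cause stated.
- "Number of days the patient went to work part-time", with the hours reduced: no cause stated.
- "Estimate child care costs due to radiation therapy": cause stated.
- "Estimate wages lost due to radiation therapy": cause stated.

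A note before the transport items says "This section is designed to capture the out of pocket expenses associated with radiation therapy".

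Section 5.1.2 requires every patient to be post-hysterectomy. Section 6.1.1 says "It is recommended that patients begin cuff brachytherapy within 16 weeks of hysterectomy". The same section allows chemotherapy: brachytherapy first is preferred, but the order is at the investigator's discretion, and if chemotherapy comes first a gap of 2 to 6 weeks is recommended.

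Section 2.2.2 lists the survey among the exploratory instruments, and Section 10.2.5 makes the exploratory analysis descriptive, without formal testing. No section says how the absence items are to be scored or summarised.

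**The concern.** The form names radiation as the cause in two items of the block and leaves it out of the other two. The patients are women who may well be off work for another reason when the window opens: recovery from surgery, or chemotherapy given beforehand. With the preferred sequence, chemotherapy can also begin inside the 40 days after brachytherapy. A woman on phased return after surgery raises the same problem for the part-time item.

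Two women in the same position can therefore give very different answers to the same question, and nothing else on the form allows the difference to be resolved afterwards. Section 3.3 gives the effect of treatment duration on patients' own costs as a reason for Cohort 2, and Section 3.3.1 wants baselines for later trials. A table of days lost that mixes causes serves neither purpose well, even if it is only descriptive.

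**Working it through.** The plan gives no figure for this item, so there is none to reproduce. The check is textual (above) plus the length of the window and an illustration.

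**Window for a 2-fraction course.** Section 6.1 puts the fractions ideally 7 days apart, and Appendix I adds 40 days.

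- Not counting the first day: 7 + 40 = 47 calendar days; 47 × 5/7 = 33.6 working days.
- Counting it: 7 + 40 + 1 = 48 calendar days; 48 × 5/7 = 34.3 working days.

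So a woman on leave throughout, who answers literally and for the whole window, enters about 33 to 34 days. If the form is collected earlier, for example at the 1-month visit in the study calendar (Section 8), the count is cut short.

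**Illustration of the mean.** Two inputs are assumed because the documents give neither: a share *f* of working women on leave throughout, and 2 days truly lost by each of the others.

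- If women on leave enter the full window: mean = 33*f* + 2(1 − *f*).
- If they enter zero: mean = 2(1 − *f*).
- If they leave it blank: mean = 2 among those who answer.

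| *f* | full window entered | zero entered | blank |
|---|---|---|---|
| 10% | 3.3 + 1.8 = 5.1 | 1.8 | 2 |
| 20% | 6.6 + 1.6 = 8.2 | 1.6 | 2 |
| 30% | 9.9 + 1.4 = 11.3 | 1.4 | 2 |

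Using 34 instead of 33 gives 5.2, 8.4 and 11.6 in the first column. The same women yield a mean of 1.4 or 11.3 days at *f* = 30%, depending only on how they read the question.

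**Window by arm.** The window grows with the length of the course. Section 6.3 caps the control course at three weeks: 21 + 40 + 1 = 62 calendar days. Three weekly control fractions (assumed spacing) give 14 + 40 + 1 = 55. Against 48 days for the 2-fraction course, that is 7 to 14 calendar days, or 5 to 10 working days, more. If the same share in each arm enters the full window, the arms differ by 0.5 to 1.0 working days at 10% and by 1.5 to 3.0 at 30%, with no effect of radiation. The plan states only upper limits for the control course, so the gap could be smaller.

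**The case against.** A reader might infer that women already on leave are scored as losing the whole window. The documents do not support that. There is no scoring rule, and such a woman could enter the full window, zero, a blank, or only her treatment days. The window opens at radiation, the section note mentions radiation and the neighbouring items name it, so some women will read the question as intended. What can be said is that the item is ambiguous.

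A reader might also infer that surgical or chemotherapy leave dominates the lost-work result. That is not supported either. The shares above are assumed, 16 weeks is a recommended upper limit, and women treated late may be back at work. Section 3.3.1 itself contrasts this population with earlier gynecologic studies strongly affected by chemotherapy.

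The reach is small. The Cohort 2 primary endpoint is FACIT-COST (Sections 10.2.1 and 10.2.3), which does not use these items, and no test of lost days is planned. The wage item is protected by its own wording. All-cause days beside radiation-attributed wages are two different measures and need not contradict each other.

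All-cause absence compared by randomised arm would be a defensible measure, and asking patients to attribute cause brings in judgement. Nor should the table be restricted to women working just before radiation. Section 11 assigns the arm at enrolment, treatment may start up to 10 business days later, and Section 4.1 describes the trial as un-blinded. Work status at that point can already reflect the assigned arm.

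These points limit the size of the concern and shape the remedy, but they do not remove the ambiguity. The note speaks of out-of-pocket expenses, which days absent are not. If all-cause absence were intended, the form and the analysis section would need to say so.

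**Conclusion.** The gap is real and minor. The full-day and part-time absence items state no cause, and the form records work status only before diagnosis, so leave for surgery or chemotherapy cannot be told apart from days lost to radiation. For one woman on leave throughout a 2-fraction course, the entry can lie anywhere from zero to about 33 or 34 working days. The effect on an arm mean is unknown. The rise from 2 to about 5 to 11 days is an illustration that rests on 10% to 30% being on leave, all of them answering literally, and 2 days lost by the others. The consequence is confined to these two exploratory, descriptively reported items. It is worth correcting because the correction is cheap and the missing information cannot be recovered later.

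**What to change.** Three changes:

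1. Add *because of radiation therapy* to both absence items, in line with the child-care and wage items below them.
2. Add one question before them: was the woman working just before she started radiation, and if not, since when and why.
3. State in Section 10.2.5 that lost days are reported for all women by randomised arm, with work status at the start of radiation shown alongside as a descriptive breakdown and not as the only analysis set.

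The cost is an amendment to the form. Attribution by the patient carries some subjectivity, which the work-status question helps to interpret. Forms already returned lack the new question and wording, so they have to be shown separately.

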Appendix J - HEALTH CARE EXPENSE DIARY FOR SURVEY COMPLETION

Use this diary to record your health care-related expenses from the time you start radiation therapy until 6 to 10 weeks after you have completed radiation therapy. A copy of the survey questions is included with this diary for your reference.

Protocol name: Short Course Adjuvant Vaginal Brachytherapy in Early Endometrial Cancer Compared to Standard of Care

Version Date: 18JUN2025

Principal Investigator: [name]

APPENDIX K. COST-FACIT**COST – FACIT (Version 2)**

Below is a list of statements that other people with your illness have said are important. **Please circle or mark one number per line to indicate your response as it applies to the past 7 days.**

		Not at all	A little bit	Some- what	Quite a bit	Very much
FT1	I know that I have enough money in savings, retirement, or assets to cover the costs of my treatment.....	0	1	2	3	4
FT2	My out-of-pocket medical expenses are more than I thought they would be.....	0	1	2	3	4
FT3	I worry about the financial problems I will have in the future as a result of my illness or treatment	0	1	2	3	4
FT4	I feel I have no choice about the amount of money I spend on care.....	0	1	2	3	4
FT5	I am frustrated that I cannot work or contribute as much as I usually do.....	0	1	2	3	4
FT6	I am satisfied with my current financial situation	0	1	2	3	4
FT7	I am able to meet my monthly expenses	0	1	2	3	4
FT8	I feel financially stressed.....	0	1	2	3	4
FT9	I am concerned about keeping my job and income, including work at home.....	0	1	2	3	4
FT10	My cancer or treatment has reduced my satisfaction with my present financial situation	0	1	2	3	4
FT11	I feel in control of my financial situation.....	0	1	2	3	4
FT12	My illness has been a financial hardship to my family and me	0	1	2	3	4
